6.1 Definitions

6.1.1 Adverse Event (AE)

An AE is any untoward medical occurrence in a patient or subject during an experiment, and which does not necessarily have a causal relationship with this treatment.

An AE can therefore be any unfavourable and unintended sign (including an abnormal laboratory finding), symptom or disease temporally associated with the use of a product, whether or not considered related to the product. Any worsening (i.e., any clinically significant adverse change in the frequency or intensity of a pre-existing condition) should be considered an AE.

6.1.2 Adverse Reaction (AR)

An AR is any untoward and unintended responses to an investigational medicinal product or to an experiment and, when an investigational product is concerned, related to any dose administered.

6.1.3 Serious Adverse Event (SAE)

An SAE is any untoward medical occurrence that results in any of the following:

- Death
- A life-threatening^a experience
- In-patient hospitalisation or prolongation of existing hospitalisation
- A persistent or significant disability or incapacity
- A congenital anomaly or birth defect
- Important medical events that may be considered an SAE when based on appropriate medical judgement they may jeopardise the subject and may require medical or surgical intervention to prevent one of the above outcomes

^a The term "life threatening" in the definition of SAE refers to an event in which the subject was at risk of death at the time of the event. It does not refer to an event which hypothetically might have caused death if it was more severe.

6.2 Adverse Events that do not require reporting

In general, the following should not be reported as AEs:

- Pre-existing conditions, including those found as a result of screening (these should be reported as medical history or concomitant illness).
- Pre-planned procedures, unless the condition for which the procedure was planned has worsened from the first trial-related activity after the subject has signed the informed consent.

The following events are commonly observed and are therefore not considered as adverse events for the purpose of the trial:

Critical illness is a severe and life-threatening condition, whereby serious events are expected to occur. Especially long-stay patients have a particularly high risk of morbidity and mortality. In daily medical practice, all medical events and procedures are recorded in a central electronic patient file. In this clinical study, only those safety parameters that could theoretically be related to the used study fluid will be documented, as well as those complications for which the treating physician judges a potential relationship. Critically ill patients with expected ICU stay of at least 5 days are inherently suffering from multiple medical conditions and are at risk of new complications. Reporting all untoward medical events would not be practically feasible neither relevant for the data. Life-threatening events occurring in the study population such as (but not restricted to) hypotension, hypoxia, coma are all typical manifestations of critical illness. Such events are thus considered as a confirmation that patient selection has been adequate (reflecting a true long-stay ICU population) and thus will not be considered as (serious) adverse event, and will not be recorded neither reported to the sponsor or the ethical committee. Nevertheless, any serious adverse reaction of which the treating physician judges a potential relationship with the used study fluid will be reported to the study sponsor.

Although these events should not be reported to the Sponsor, these should be recorded in the patient's medical notes according to routine practice.

The following events not to be considered as SAEs are:

- Pre-planned hospitalisations unless the condition for which the hospitalisation was planned has worsened from the first trial-related activity after the subject has signed the informed consent.
- Hospitalisation as part of a standard procedure for protocol therapy administration. However, hospitalisation or prolonged hospitalisation for a complication of therapy administration will be reported as an SAE.
- Hospitalisation or prolongation of hospitalisation for technical, practical, or social reasons, in absence of an AE.
- Mortality or 'serious' outcome related to disease progression.

6.3 Recording of adverse events (AEs)

There are no known risks associated with the study-specific intervention (oral ketone administration). The participant will be asked to report any adverse event related to the study-specific intervention to the study team. These reported events will be documented by the Investigator in the source documents and reported to the Sponsor through the (e)CRF.

The following minimum information should be recorded for each adverse reaction (AR):

- AE description
- start and stop date of the AR
- severity
- seriousness
- causality assessment to the study interventions
- outcome

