Title of clinical Trial («Trial»)	A single-centre, placebo-controlled, cross-over randomized controlled trial evaluating the metabolic effects of a ketone ester food supplement in intensive care patients: The KETOCARE RCT		
Protocol Short Title Acronym	The KETOCARE RCT		
Sponsor name	University Hospitals Leuven (UZ Leuven)		
Coordinating Investigator	[name]. [name]		
Contact Address Cl	[name]		
Contact Email Cl	[contact]		
Contact Phone CI	[name]		
Public database nbr	ISRCTN: 13903536		
Sub Investigators	[name]. [name] (UZ Leuven) [name]. [name] (KU Leuven) [name]. [name] (UZ Leuven)		
Medical condition or disease under investigation	Adult critical illness		
Trial rationale	To study the feasibility, safety and tolerability of enteral ketone ester supplementation to increase circulating ketone levels in adult critically ill patients.		
Primary objective	To identify a supplementation dose of enteral ketone esters that is able to increase circulating 3-hydroxybutyrate concentrations in adult crtitically ill patients by at least 0.22 mmol/l.		
Secondary objective(s)	To demonstrate that supplementation of enteral ketone esters is safe.		
Trial Design	Single-center, placebo-controlled, cross-over randomized controlled trial		
	- An increase in plasma 3-hydroxybutyrate by at least 0.22 mmol/l following administration of enteral 3HHB (E)		
	- Plasma levels of 3HHB and metabolites 3-hydroxybutyrate and 1,3- butanediol over time during (6 hour period) and after the intervention (18 hour period) (E)		
Endpoints	- Urine levels of 3HHB and metabolites 3-hydroxybutyrate and 1,3- butanediol over time during (6 hour period) and after the intervention (18 hour period) (E)		
(Efficacy = E;	- Blood glucose concentrations during the 48h-study period (E)		
Safety – S, Tolerability – T)	- Incidence of ketoacidosis during the intervention window and until 18h after stopping study infusion (S		
	- Intolerance for the supplement (including abdominal discomfort or vomiting) (S/T)		
	- Incidence of severe (<40 mg/dl) hypoglycemia during the intervention window and until 18h after stopping study infusion (3HHB or placebo) (S)		
Sample Size	16 patients for each study dose completing the 48h study period (maximum of 48 patients completing the 48h study period in total)		

Dietary supplement, dosage and route of administration	Enteral administration of a ketone ester supplement (3-HHB) in increasing dosage (25g, 50g, 75g)		

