Preclinical research by our group further strengthens the **potential clinical benefit of increasing plasma 3-hydroxybutyrate in critically ill patients**. Indeed, in a mouse model of sepsis-induced prolonged critical illness, we demonstrated that exogenous administration of the ketone body 3-hydroxybutyrate, administered as daily bolus injections of a racemic mixture of R,S-3-hydroxybutyrate sodium salt (3HB-Na), significantly attenuated the development of muscle weakness [7]. Subsequent dose-response and toxicity studies revealed that ketone esters are preferred to ketone salts, with a broader therapeutic window [8]. Indeed, the effective dose of 5g/kg/day of the ketone salt 3HB-Na was close to the toxic threshold [9], whereby increased morbidity and mortality by increased doses are likely explained by excessive sodium intake, since ketone esters have a substantially higher threshold for toxicity.

A potentially **safer alternative** for ketone salts is the ketone ester R-3-hydroxybutyl-R-3hydroxybutanoate (**3HHB**) which is endogenously converted to two 3-hydroxybutyrate molecules [10]. The ketone ester is hydrolyzed to 3-hydroxybutyrate and 1,3-butanediol by esterases that are located in the circulation, in the gastro-intestinal tract, the liver, and other tissues [11]. The butanediol molecule is further metabolized to 3-hydroxybutyrate in the liver by alcohol and aldehyde dehydrogenases [11, 12]. We demonstrated that treatment of septic mice with the ketone ester 3HHB **improved muscle weakness** from a dose of 3.5 g/kg/day onward [13]. Up to a dose of 7 g/kg/day 3HHB, signs of organ damage or liver toxicity were absent. However, septic mice showed a higher peak plasma concentration and slower 3-hydroxybutyrate clearance than healthy control mice, leading to toxicity with a bolus of 14 g/kg/day. **This toxicity of a single bolus was completely avoided by a continuous intravenous infusion of this dose** (i.e. 14 g/kg/day) over 24h, while the protective effect on muscle weakness remained equally present [13]. This preclinical research has led to a patent application PCT/EP2017/081394 which is currently in its national phase.

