2.3 Secondary Endpoints

- Plasma levels of 3HHB and metabolites 3-hydroxybutyrate and 1,3-butanediol over time during (6 hour period) and after the intervention (12 hour period)
- Urine levels of 3HHB and metabolites 3-hydroxybutyrate and 1,3-butanediol over time during (6 hour period) and after the intervention (12 hour period)
- Plasma levels of cholesterol (HDL, LDL, total), triglycerides en free fatty acids over time during (6 hour period) and after the intervention (12 hour period)
- Blood glucose concentrations during the 48h-study period
- Incidence of severe (<40 mg/dl) hypoglycemia during the intervention window and until 12h after stopping study infusion (3HHB or placebo)
- Incidence of ketoacidosis during the intervention window and until 12h after stopping study infusion
- Intolerance for the supplement (including abdominal discomfort or vomiting)

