2.4 Trial Design

This will be a single center trial, in adult critically ill patients. With a cross-over design (Fig. 1), patients will receive in random order on 2 consecutive days 3HHB and placebo.

Patients will receive the investigational product between ICU day 4 and 14, to avoid the time of increase in endogenous ketogenesis that we have previously documented to be present in the first 2 to 3 days in ICU [6]. The investigational product (3HHB) or placebo will be delivered through the enteral feeding tube.

Figure 1: Cross-over design of the trial. In group 1, participants will receive 3HHB on intervention day 1, followed by a placebo on intervention day 2. Group 2 will receive placebo on intervention day 1 and 3HHB on intervention day 2. Repetitive blood sampling is indicated in red.

Patients are typically started on enteral nutrition (EN) within 48 hours of admission, unless they are able to eat. EN is delivered for 2x10h per day (8am-6pm and 8pm-6am), with 2x2h interruption (6-8am and 6-8pm) to measure gastric residual volume (Fig 2). EN is usually started at a low rate, and increased depending on tolerance (as deducted in part from gastric residual volumes). For this trial, the caloric intake will be kept constant over the 2 intervention days avoiding the influence of caloric intake on outcome measures. Patients with nasogastric tubes who are not receiving enteral nutrition are also eligible for inclusion. This will allow to study ketone absorption and clearance in both fed and unfed state in the critically ill patient.

Figure 2: 10 hour feeding scheme. Intermittent administration of 3HHB/placebo (in green) every hour for 6 times.

We will administer 3HHB or placebo via repeated small boluses through the nasogastric feeding tube, as is also done for enterally administered medication. The nasogastric tube will be flushed with a 5% glucose solution prior and after administration of 3HBB or placebo to ensure that the bolus has completely entered the stomach while also avoiding clotting of the nasogastric tube.

The first bolus wil be given at 10 am (after 2 hours of enteral feeding) and this wil be repeated 5 times with one hour interval (6 doses in total). After the last bolus, the patient will be fed for three more hours. The next day, this procedure will be repeated (Fig. 1).

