We will first perform this trial with a 25 g dose of 3HHB divided over 6 boluses. The density of 3HHB is 1.07 g/ml, 25 g has a volume of 23.4 ml, so each bolus consist of 3.9 ml 3HHB. Next, we will assess the primary and secondary endpoints in this cohort of patients. If the dose of 25 g is found safe but ineffective for increasing plasma 3-hydroxybutyrate at least with 0.22 mmol/l, a second cohort of patients will be tested with the same cross-over study design but with a higher 3HHB dose (50 g of 3HHB, divided over 6 boluses of 7,8 ml). If this dose is again safe but ineffective, a third cohort of patients will be tested with the same cross-over study design with an increased dose of 75 g of 3HHB, divided over 6 doses of 11.7ml. For each cohort of patients tested (cohort I to test 25 g, cohort 2 to test 50 g and cohort 3 to test 75 g),

16 patients will be included. If a patient is not able to complete the 48h study period (e.g. due to consent withdrawal or due to unplanned surgery or other procedures) and this is not related to safety concerns that are directly attributed to the intervention, an extra patient will be included in order not to compromize the statistical power of the study.

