4.1 Participant consent and withdrawal of consent

The Trial will be conducted only on the basis of prior informed consent by the Trial participants and/or their legally authorized representative(s). As such, no Trial-related procedures will be conducted prior to obtaining written informed consent from potential Trial participants.

In the majority of patients, we expect that informed consent will have to be obtained from the patient's closest family member or legal representative due to the nature of their illness. As regaining consciousness and mental competence often occurs gradually and slowly in these patients, it is very difficult to determine at what time the patient is able to give a valid informed consent. In addition, recovery can take from several days to several months. Often, patients are only able to give a valid consent after discharge from ICU, at what time the intervention is already terminated. Therefore, we will give an opting out form to the legal representative, who can give it to the patient once he/she is well recovered. With this document, the patient has the possibility to terminate the study intervention (if still applicable) and/or withdraw from further data collection.

The process for obtaining and documenting initial and continued informed consent from potential Trial participants will be conducted in accordance with ICH-GCP E6(R2), applicable regulatory requirements and internal Standard Operating Procedures (SOPs).

All originally signed obtained Informed Consent Forms (ICFs) must be retained/archived in the Trial Master File (TMF) and must not be destroyed (even when a scanned copy is available) before expiration of the legal archiving term as defined in the protocol section entitled "Archiving".

Participants may voluntarily withdraw consent to participate in the Trial for any reason at any time. The participant's request to withdraw from the Trial must always be respected without prejudice or

consequence to further treatment. Consent withdrawal will be documented in the participant's medical record.

Trial data collected before withdrawal can be used in the trial. Results of analyses on samples obtained before withdrawal of consent can also be used. No new trial data or samples will be collected after withdrawal of the participant. No new analysis on samples will be performed after withdrawal.

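### Intolerance is captured by self-report and attribution in patients who mostly lack capacity, and 16 patients per dose can describe safety but not demonstrate it

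*Protocol*

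**What the plan says.** **Endpoint and objective.** Section 2.3 of the protocol lists as a secondary endpoint "Intolerance for the supplement (including abdominal discomfort or vomiting". The Trial Synopsis gives the secondary objective as "To demonstrate that supplementation of enteral ketone esters is safe".

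**How events are collected.** Section 6.3 states: "The participant will be asked to report any adverse event related to the study-specific intervention to the study team". The minimum information it then requires is set out per adverse reaction. Section 6.2 adds two routes: safety parameters that could in theory be linked to the study fluid, which are not listed there, and complications that the treating physician thinks may be linked to it. The data list in section 8.2 has an item for adverse reactions, but none for vomiting, abdominal discomfort or gastric residual volume.

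**Who the participants are.** Section 4.1 states: "In the majority of patients, we expect that informed consent will have to be obtained from" a close relative or legal representative. It adds that valid consent is often possible only after ICU discharge, when the intervention has ended.

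**What the unit already measures.** Section 2.4 describes enteral feeding "with 2x2h interruption (6-8am and 6-8pm) to measure gastric residual volume", and says that tolerance is judged in part from these volumes.

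**What depends on the data.** Section 2.4 starts the next cohort on this condition: "If the dose of 25 g is found safe but ineffective for increasing plasma 3-hydroxybutyrate at least with 0.22 mmol/l".

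**Known risks.** Section 6.3 opens with "There are no known risks associated with the study-specific intervention (oral ketone administration". Section 1 reports higher peaks and slower clearance in septic mice, "leading to toxicity with a bolus of 14 g/kg/day".

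**The concern.** A tolerability endpoint is only as good as the way its events are found. Here the named source is the patient, in a population that the protocol itself expects mostly to lack capacity during the two study days. The patient is also asked to report only events that are already related, so a causal judgement comes before the count. The crossover offers an unbiased alternative, which is to count the same signs on the 3HHB day and the placebo day and compare. That works fully only if the signs are recorded on both days whatever anyone thinks caused them.

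The count is also used. A dose must be found safe before a higher one is tested, and intolerance is among the endpoints assessed at that point. Missing bedside observations cannot be restored by an analysis plan. Finally, an objective to demonstrate safety asks more of 16 patients than any result from them could give.

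**Working it through.** **1. Which safety data depend on self-report or attribution**

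| Item | Where | Needs self-report or attribution? |
|---|---|---|
| Severe hypoglycaemia, ketoacidosis | 2.3 | No |
| Glucose and ketones at 4-hour intervals | 2.5, 8.2 | No |
| Routine blood gas results | 8.2 | No |
| Cumulative enteral intake | 8.2 | No |
| All deaths up to 48 h past the study period | 6.4 | No |
| Abdominal discomfort | 2.3, 6.3 | Yes: patient report, then relatedness |
| Vomiting | 2.3, 8.2 | Visible to staff, but the only listed field is adverse reactions |
| Gastric residual volume | 2.4 | Measured in routine care, but not in the endpoint or the data list |
| Other complications | 6.2 | Yes, unless among the unlisted safety parameters |

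The gap is therefore in tolerability and in events that resemble critical illness.

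**2. Timing of the residual volumes.** The first bolus is at 10 am and five more follow hourly, so the last is at 3 pm. Feeding runs three more hours, to 6 pm. The 6-8 pm residual follows dosing on the same day. The 6-8 am residual comes before the next 10 am bolus. Both can be assigned to a study day.

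**3. Who is counted.** Section 2.4 replaces a non-completer unless the reason is a safety concern directly attributed to the intervention. Section 7.2 bases the primary analysis on completers and puts shorter study periods in a sensitivity analysis. A patient who stops for intolerance that nobody attributes to the product is thus replaced and leaves the primary set.

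**4. Where 16 comes from.** Section 7.1 gives an effect size of 0.22/0.28 = 0.786, a paired t-test, 95% certainty and 80% power. With a two-sided 5% level (assumed) and the noncentral t distribution, n = 15 gives 80.8% and n = 16 gives 83.6%. The stated 16 is consistent with this efficacy calculation. No safety quantity enters it.

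**5. What 16 patients can say about an event rate**

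- 0 of 16, two-sided 95% upper limit: 1 − 0.025^(1/16) = 20.6%.
- 0 of 16, one-sided 95% upper limit: 1 − 0.05^(1/16) = 17.1%.
- 1 of 16, two-sided exact upper limit: 30.2%.
- Chance of at least one event at a true rate of 20%: 1 − 0.80^16 = 97%.
- Patients needed, all without an event, to exclude a rate of 10% (one-sided 95%): ln 0.05 / ln 0.90 = 28.4, so 29. To exclude 5%: ln 0.05 / ln 0.95 = 58.4, so 59. These target rates are illustrations and are not in the protocol.

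**6. Effect of missed events.** The chance that a cohort shows no event is (1 − p·s)^16, where p is the true rate and s the share detected. The protocol gives neither, so both are assumed over a range.

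| True rate p | s = 100% | s = 75% | s = 50% | s = 25% |
|---|---|---|---|---|
| 10% | 18.5% | 28.7% | 44.0% | 66.7% |
| 20% | 2.8% | 7.4% | 18.5% | 44.0% |
| 30% | 0.3% | 1.7% | 7.4% | 28.7% |

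**7. Within-patient comparison.** An exact two-sided McNemar test on 16 pairs needs at least 6 discordant pairs, all in one direction (2 × 0.5^6 = 0.031; five give 0.0625). If events occur only on the 3HHB day, power is 8% at a 20% rate and 34% at a 30% rate. The comparison is worth making, but as a description.

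**8. Known risks.** Section 6.3 says none are known. Section 1 reports slower clearance and bolus toxicity in septic mice, the model closest to the trial population. The two statements do not fit as worded.

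**The case against.** The case against has real weight.

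- **Much of the safety data is objective.** This is right, as the first table shows. It limits the point to tolerability and does not remove it.
- **Section 6.2 also documents safety parameters without attribution.** Vomiting could be one of them. But they are not listed, and section 8.2 has no field for it.
- **Lack of capacity to consent is not inability to report discomfort.** This stands too. Section 4.1 is about valid consent and describes a gradual return, so some patients can report. Self-report is incomplete here, not impossible.
- **Feeding intake is already collected.** In part. Cumulative intake does not show when or why feeding was interrupted, and section 2.4 intends it to be constant over the two days.
- **Residual volume as a sign of intolerance is a clinical choice.** Yes, but section 2.4 already treats it as one.

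A reader might also draw three stronger conclusions that the documents do not support.

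- *That an unsafe dose will pass too easily.* Section 2.4 states no safety threshold, so no probability of passing can be calculated. The table of missed events shows a direction under assumed rates and is not a forecast.
- *That the placebo day cannot serve as a control.* Measured safety data are collected on both days, and an event could be attributed to the study fluid on either. The comparison is weakened for intolerance, not lost.
- *That the toxic mouse dose, scaled to humans, shows the highest trial dose to be hazardous.* That sets a total given in six hourly boluses against a single bolus. Section 1 adds that continuous infusion of the same mouse dose avoided the toxicity, and section 2.1 cites safe use in healthy adults up to 2.142 g/kg/day.

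**Conclusion.** The point holds for tolerability. As written, the plan will tend to under-count intolerance and filter it by attribution, and the result enters the decision that a dose was safe. The size of the under-count is unknown because the protocol gives no detection rate. If half of all events were missed, a true rate of 20% would leave a cohort of 16 without a recorded event 18.5% of the time, against 2.8% with full detection.

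The objection to the word demonstrate rests on no assumption about detection. Even a perfect record of no event in 16 leaves a rate of up to 20.6% (17.1% one-sided) open. Sixteen patients can reveal frequent harm and cannot establish safety. The statement on known risks conflicts with section 1 and has to be reconciled. The weight is moderate: the efficacy result and the laboratory safety endpoints are untouched.

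**What to change.** - **Sections 2.3, 6.3 and 8.2.** Record staff-observed vomiting, the scheduled gastric residual volumes and any interruption of feeding. Do so on both study days, regardless of attribution, in all dosed patients including those who do not complete 48 hours. Patients with a tube who are not fed enterally are eligible, so state how the feeding-related items are handled for them.
- **Discomfort.** Take it only from patients able to report it, and give that number as the denominator.
- **Analysis.** Compare the 3HHB day with the placebo day within patient, as a description.
- **Secondary objective.** Replace demonstrate with describe, for safety and tolerability, with exact 95% confidence intervals per dose.
- **Section 6.3.** Reconcile the statement on known risks with the septic-mouse findings in section 1.

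What counts as safe for the next cohort remains for the sponsor to set. The cost is a few eCRF fields, filled from the existing electronic patient file, some changes of wording, and a more modest safety claim.
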